#### Part 2 Age Group 2 (PK)

The population PK Model will be updated with sparse PK data from a subset of Part 2 Group 2 patients for the purpose of further confirming the target dose for Age Group 2. This will be performed prior to database lock and requires unblinding, and as such will be done by an unblinded team who is not involved in the conduct of the study.

#### 9.5.2 Safety variables

Safety data from Part 1 (PK/PD) and Part 2 (Efficacy) will be presented separately.

The assessment of safety will be based primarily on the frequency of AEs, SAEs, and laboratory abnormalities. Other safety data, such as specific adverse events of interest (i.e. hypotension, hyperkalemia, renal impairment, angioedema), will be summarized as appropriate.

The incidence of treatment-emergent AEs (new or worsened) will be summarized by primary system organ class, preferred term, severity, and relationship to study drug. In addition, the incidence of death, SAEs, and AEs leading to discontinuation will be summarized separately by primary system organ class and preferred term.

Laboratory data will be summarized by presenting shift tables using extended normal ranges (baseline to most extreme post-baseline value), by presenting summary statistics of raw data and change from baseline values (mean, medians, standard deviations, ranges) and by the flagging of notable values in data listings.

Data from other tests (e.g. vital signs) will be descriptively summarized as appropriate by presenting absolute values and change from baseline at each assessment time point. Any other information collected will be listed as appropriate.

Safety analyses will be performed based on all patients who received study drug during Part 1 and the safety population for Part 2 (Efficacy). There will be no formal statistical inference analysis.

#### 9.5.3 Biomarkers

Data for each biomarker will be summarized by treatment group and time point using descriptive statistics (n, mean, median, SD, min, max, n below LLOQ, n above ULOQ, geometric mean and 95% confidence interval around the geometric mean). Summary statistics for change from baseline at each time point will also be presented.

In addition, as a supportive analysis, the same MMRM analysis as above will be performed using data from all post-baseline scheduled visits (Week 4, Week 8, Week 12 and Week 52).

#### 9.5.4 PK/PD

The relationship between LBQ657 exposure to changes in plasma BNP, plasma NTproBNP and plasma cGMP will be explored using exposure-response models.

#### 9.6 Interim analyses

An external DMC will monitor patient safety data during the course of the study. For this study, the DMC will review safety data on a regular frequency, e.g. every six months. DMC may request additional safety data review. Such safety analyses do not inflate the type I error for the primary efficacy hypothesis testing and thus require no multiplicity adjustments.

#### Part 1 (PK/PD)

The available PK, PD and safety data from each age group will be analyzed to confirm the dose for that age group in Part 2 and to start the next younger age group in Part 1. A sample size of up to 12 observations per age group for Groups 1 and 2 is prospectively planned to evaluate the PK and PD of LCZ696 analytes following single dose administration of LCZ696 0.8 mg/kg (N=6 observations) and LCZ696 3.1 mg/kg (N=6 observations). For Group 3 a sample size of up to 8 observations is prospectively planned to evaluate the PK and PD of LCZ696 analytes following single dose administration of LCZ696 0.4 mg/kg (N= approximately 4 observations) and LCZ696 1.6 mg/kg (N= approximately 4 observations). Since the pharmacokinetics of LCZ696 is demonstrated to be dose independent, dose-normalized PK parameters from both dose cohorts will be combined. If no age effect on PK is observed, then data from two different groups may be pooled.

#### Part 2 (Efficacy)

#### Interim efficacy analysis of the global rank endpoint

It is planned to have a formal interim efficacy analysis. The interim efficacy analysis is planned when at least 180 patients (at least 36 patients from each age group) have completed the study (i.e., reached a terminal endpoint or completed the 1 year study visit), and at least 40 patients have had an event in Category 1 or 2. Some adjustment to the time of interim analysis may be made to coincide with the regular DMC meetings. One-sided tests will be performed and appropriate statistical adjustments for the interim efficacy analysis actually performed will be made to ensure the overall one-sided type I error of 0.025 (Lan-DeMets spending function to match an O'Brien-Fleming stopping boundary). For the interim efficacy analysis, the analysis dataset will comprise all patients who completed the study by the cut-off date.

The trial may only be concluded early for efficacy, if a significant difference between two treatment arms for the primary efficacy endpoint is achieved by crossing the pre-specified boundary at the interim efficacy analysis and the overall risk/benefit profile is considered positive. A futility analysis will also be incorporated into the interim analysis plan, whereby the study can be stopped if there is evidence that the study is unlikely to have a positive outcome. Details of the stopping rules for the futility analysis will be described in the interim analysis statistical plan.

The interim analysis will be performed by an external independent statistician at an external data analysis center, who will not be involved in the study conduct. The results will be reviewed by the independent DMC. Investigators and others who are involved in the conduct of the trial and in the analysis of the final trial results, or who have contact with study centers, will remain blinded to the treatment codes and interim analysis results until all monitoring decisions have been made and the database has been unblinded for final analysis. Additional details of the interim analysis plan for efficacy and safety will be described in the [DMC charter].

If the study is stopped early at interim analysis due to overwhelming efficacy, then the prespecified percentage of patients will be used for this analysis. Additional sensitivity analysis for the primary global rank endpoint (and components) will be performed at time points of 30 days, 90 days, and 180 days. For time to event endpoints, annualized event rates will be calculated.

### 9.7 Sample size calculation

#### Part 1 (PK/PD)

From a prior clinical study in adult HF patients, the observed CV% for body-weight normalized LBQ657 exposure was 37.1%, and the observed CV% for body-weight normalized clearance and volume of distribution of valsartan was 39.4% and 49.6%, respectively (Study CLCZ696A2117). Therefore, 49.6% of CV% was assumed for sample size estimations. A sample size of 12 observations (except Group 3 where N—approximately 8 observations) is expected to have 80% probability that the 95% CI of the point estimate for the geometric mean estimates of clearance and volume of distribution will be between 60% and 140% range (95% CI: 71 – 141%).

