# 3 Investigational plan

# 3.1 Study design

This study uses a seamless design which consists of two parts (Figure 3-1):

**Part 1**: This is a multi-center, open-label, study in pediatric patients (1 month to <18 years) with HF (LVEF  $\le 45\%$  or LV fractional shortening  $\le 22.5\%$ ).

A screening epoch of up to 3 weeks will be used to assess eligibility. Eligible patients who participate in this open-label PK/PD assessment will be placed into three Groups based on age (Group 1: 6 to < 18 years, Group 2: 1 to < 6 years, and Group 3: 1 month to < 1 year). To ensure that patients are enrolled in both high and low end of the 6 to < 18 years of age group, approximately 50% patients will be enrolled who are 6 to 11 years of age in Group 1.

The following stepwise recruitment will be utilized:

- Group 1 (6 to < 18 years): A sample size of at least 6 patients will be prospectively planned to be recruited to evaluate PK and PD of LCZ696 analytes following the single dose administration of LCZ696 0.8 mg/kg (N=6 observations) and then the single dose administration of LCZ696 3.1 mg/kg (N=6 observations). The patients who receive the LCZ696 single dose of 0.8 mg/kg treatment will also have an option to subsequently receive the LCZ696 3.1 mg/kg dose. If a patient who received the LCZ696 0.8 mg/kg does not qualify or declines to receive the LCZ696 3.1 mg/kg dose, an additional patient will be recruited to receive the LCZ696 3.1 mg/kg dose.
- Group 2 (1 to < 6 years): A sample size of at least 6 patients will be prospectively planned to be recruited to evaluate PK and PD of LCZ696 analytes following the single dose administration of LCZ696 0.8 mg/kg (N=6 observations) and then the single dose administration of LCZ696 3.1 mg/kg (N=6 observations). The patients who receive LCZ696 single dose of 0.8 mg/kg treatment will have an option to receive LCZ696 3.1 mg/kg dose subsequently. If a patient who received the LCZ696 0.8 mg/kg dose does not qualify or declines to receive the LCZ696 3.1 mg/kg dose, an additional patient will be recruited to receive the LCZ696 3.1 mg/kg dose.

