• Group 3 (1 month to < 1 year): A sample size of at least 4 patients will be prospectively planned to be recruited to evaluate PK and PD of LCZ696 analytes following the single dose administration of LCZ696 0.4 mg/kg (N= approximately 4 observations) and then the single dose administration of LCZ696 1.6 mg/kg (N= approximately 4 observations). The patients who receive LCZ696 single dose of 0.4 mg/kg treatment will have an option to receive LCZ696 1.6 mg/kg dose subsequently. If a patient who received the LCZ696 0.4 mg/kg dose does not qualify or declines to receive the LCZ696 1.6 mg/kg dose, an additional patient will be recruited to receive the LCZ696 1.6 mg/kg dose.

Available PK/PD and safety data will be reviewed to confirm or modify the doses tested for each age group (Section 3.5 and Section 9.4.1).

If deemed necessary for dose determination for Part 2, additional age group 3 patients may be enrolled in Part 1.

Eligible patients will first receive the LCZ696 0.4 mg/kg single dose (Group 3) or 0.8 mg/kg single dose (Group 1 or 2). Patients must be currently treated with an ACEI or ARB (at any dose) at screening to be eligible for the LCZ696 0.4 mg/kg (Group 3) or 0.8 mg/kg (Group 1 and 2) single dose.

To be eligible for the subsequent LCZ696 3.1 mg/kg dose, patients in Group 1 or 2 must be currently treated with a daily dose equivalent of at least enalapril 0.2 mg/kg (Table 3-1) prior to the LCZ696 3.1 mg/kg (Group 1 and 2) single dose assessment.

To be eligible for the subsequent LCZ696 1.6 mg/kg dose, patients in Group 3 must be currently treated with a daily dose equivalent of at least enalapril 0.1 mg/kg (Table 3-1) prior to the LCZ696 1.6 mg/kg single dose assessment.

If a patient who has completed the LCZ696 0.4 mg/kg or 0.8 mg/kg single dose does not participate in the LCZ696 1.6 mg/kg or 3.1 mg/kg dose, the next eligible replacement patient may be enrolled to directly receive the LCZ696 1.6 mg/kg or 3.1 mg/kg dose, respectively.

The LCZ696 1.6 mg/kg or 3.1 mg/kg dose can be administered after a minimum of 5 days following the LCZ696 0.4 mg/kg or 0.8 mg/kg dose, respectively (to allow for washout of the LCZ696 analytes from the first dose).

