# 3.5 Rationale for dose/regimen, route of administration and duration of treatment

## Rationale for dose selection

The approach for dose selection examines safety, PK, and PD responses following administration of two doses equivalent to adult LCZ696 50 mg (lowest) and 200 mg (highest) doses, respectively. The objective is to select a dose that provides similar exposures of LCZ696 analytes to that observed in adult heart failure patients and that maximizes neprilysin inhibition. The PD effect of neprilysin inhibition in children will be assessed through the measurement of urine and plasma biomarkers.

For the estimation of precision for pharmacokinetic parameters, data obtained from both dose levels will be pooled as pharmacokinetics of LCZ696 analytes is dose-independent (dose linearity has been established). Dose-exposure response for pharmacodynamics parameters will be compared with available adult data.

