### 9.4 Analysis of the primary variable(s)

#### 9.4.1 Variable(s)

#### Part 1 (PK/PD)

The objective of Part 1 of the study is to characterize PK and PD of LCZ696 in pediatric patients and compare PK, PD, and exposure-response with observed data in adult heart failure patients in order to determine the dose for Part 2 (Efficacy) of the study. In Part 1 (PK/PD) of the study, the pediatric patient population is divided into three age groups; Group 1: 6 to < 18 years old, Group 2: 1 to < 6 years old, and Group 3: 1 month to < 1 year old.

Considering various factors including factors such as ontogeny of enzymes/transporters, the variability in PK parameters is assumed to be similar between adult and pediatric HF patients (>3 months). Since LBQ657 is a metabolite, clearance and volume of distribution were not estimated in earlier clinical trials and coefficient of variation% (CV%) of total exposure was considered for sample size estimation. From previous clinical study in adult HF patients, the observed CV% for body-weight normalized LBQ657 exposure was 37.1% and the observed CV% for body-weight normalized clearance and volume of distribution of valsartan was 39.4% and 49.6%, respectively (CLCZ696A2117). Therefore 49.6% of CV% was assumed for sample size estimations. The sample size is up to 12 observations per age group (except Group 3 where N= 8 observations) to achieve 95% CI for geometric mean of PK parameters to fall between 60% and 140% range (95% CI: 71 – 141%) with 80% coverage probability.

A population PK model will be developed to describe incoming data from pediatric patients based on an established model developed for the adult HF population. The fidelity of the developed PK model will be cross validated for its robustness and precision to the observed data. The steady state population PK parameters including clearance, volume of distribution, Ka, T1/2, Cmax, Cmin, and AUC will be estimated. The impact of covariates such as eGFR, age, body weight, NYHA/Ross class, TBL, and AST levels will be evaluated.

Pharmacodynamic evaluations will include analysis of change in plasma cGMP, plasma BNP, plasma NTproBNP and urine cGMP. Dose and exposure-response relationship will be evaluated based on changes in plasma cGMP levels (and also plasma NTproBNP, plasma BNP, urine cGMP).

PKPD modeling of Part 1 data may be carried out, depending on the robustness of both the PK and biomarkers to be used to inform the dose justification for Part 2.

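### The Part 1 precision statement (80% probability, 95% CI within 60-140%) holds in effect for 12 observations but not for Group 3's 8: at the planning CV of 49.6% the probability is about 36%

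*Protocol*

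**What the plan says.** Protocol Section 9.7 (Part 1) quotes three CVs from an adult heart failure study: 37.1% for LBQ657 exposure, 39.4% for valsartan clearance and 49.6% for valsartan volume of distribution. It plans on 49.6%. It then says that 12 observations, or approximately 8 in Group 3, "is expected to have 80% probability that the 95% CI of the point estimate for the geometric mean estimates of clearance" and volume of distribution lies between 60% and 140%, and prints 71-141% as the interval.

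Section 9.4.1 makes the same statement: "The sample size is up to 12 observations per age group (except Group 3 where N= 8 observations"), followed directly by the same target and the same 80%. Neither section gives a separate CV, interval or probability for Group 3.

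Three other provisions bear on how the observations arise:

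- Section 3.5: "For the estimation of precision for pharmacokinetic parameters, data obtained from both dose levels will be pooled". Section 9.6 likewise says that "dose-normalized PK parameters from both dose cohorts will be combined".
- Section 3.1: a Group 1 child given the lower dose "will also have an option to subsequently receive the LCZ696 3.1 mg/kg dose", with matching options in Groups 2 and 3. For Group 3, "A sample size of at least 4 patients will be prospectively planned", against about 4 observations at each of two doses.
- Section 3.1: "If deemed necessary for dose determination for Part 2, additional age group 3 patients may be enrolled in Part 1". Section 9.6: "If no age effect on PK is observed, then data from two different groups may be pooled".

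**The concern.** The bracket changes only the number of observations for Group 3. The target, the probability and the printed interval carry over unchanged. Cutting the number from 12 to 8 at the same CV must widen the interval, so one figure cannot describe both. A reader would take 71-141% with 80% probability as the planned precision for infants under 1 year. Section 8.5 plans a DMC review of about 8 observations in that group to support its Part 2 dose recommendation. What is at stake is whether the stated design property is true for Group 3. No decision rule is tied to the 60-140% window.

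**Working it through.** **Inputs** (Sections 9.4.1 and 9.7): CV 49.6% for planning, with 39.4% and 37.1% also quoted; n = 12, or 8 in Group 3; 95% CI; 80% probability; window 60-140%; printed interval 71-141%. The protocol names no method. Observations are treated as independent.

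**Method.** For a log-normal PK parameter:

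- SD on the log scale: σ = √ln(1 + CV²). This gives 0.4690, 0.3799 and 0.3591 at CV 49.6%, 39.4% and 37.1%.
- Half-width not exceeded with 80% probability: h = t(0.975, n−1) × σ × √[χ²(0.80, n−1)/(n−1)] / √n. The interval, relative to the estimate, is exp(−h) to exp(+h).
- Probability that the upper limit is at most U: the χ² distribution function with n−1 df at (n−1) × [ln U × √n / (t × σ)]². The upper limit is the one that binds, because ln 1.4 = 0.336 is smaller than −ln 0.6 = 0.511.

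**Step 1. Reproduce the plan's figure (n = 12, CV 49.6%).** t = 2.201 and χ²(0.80, 11) = 14.63.

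- h = 2.201 × 0.4690 × √(14.63/11) / √12 = 0.3437, so the interval is 70.9% to 141.0%. This matches 71-141%.
- The probability is 80.0% against 141% and 76.8% against 140%.

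Three other 80%-assurance forms do not match at n = 12: a z-interval gives 73.6-135.8%, the CV used directly as log SD gives 69.5-143.8%, and both together give 72.3-138.2%.

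**Step 2. Apply the same method to Group 3 (n = 8, CV 49.6%).** t = 2.365 and χ²(0.80, 7) = 9.803.

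- h = 2.365 × 0.4690 × √(9.803/7) / √8 = 0.4640, so the interval is 62.9% to 159.0%.
- For U = 1.40: 7 × [0.3365 × 2.828 / (2.365 × 0.4690)]² = 5.155, which gives 35.9%. For U = 1.41 the probability is 38.6%.

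**Step 3. Sensitivity to the CV and to one more observation.**

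| n | CV | 80%-probability interval | Within 140% | Within 141% |
|---|---|---|---|---|
| 8 | 49.6% | 62.9-159.0% | 36% | 39% |
| 8 | 39.4% | 68.7-145.6% | 65% | 68% |
| 8 | 37.1% | 70.1-142.7% | 73% | 76% |
| 9 | 49.6% | 65.5-152.7% | 46% | 49% |
| 9 | 39.4% | 71.0-140.9% | 78% | 80% |
| 9 | 37.1% | 72.3-138.3% | 84% | 87% |

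At CV 49.6%, 13 observations are needed for 80% against 140%.

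**The case against.** **"Except" takes Group 3 out of the claim.** On this reading the 80% is stated only for 12 observations. Section 9.4.1 does not support that: the bracket gives N = 8 and the sentence runs straight on to the target. Even if Group 3 were exempt, the plan would then state no precision for it, and the same added sentence would be needed.

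**The method is inferred.** This is true, and some other formulas would pass at n = 8 for the two lower CVs. For example, a log-scale z-interval gives 88% at CV 39.4% and 92% at 37.1%. None of the other forms tried reproduces 71-141% at n = 12. At CV 49.6%, n = 8 fails under every variant tried that applies the 140% upper limit.

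**A reader might infer that the target is missed whatever CV is used.** With exactly 8 observations it is, but that is not a firm conclusion. Section 9.7 says approximately 8, and 9 observations give 78% at CV 39.4% and 84% at CV 37.1%. The 37.1% also belongs to LBQ657 exposure, not to the clearance and volume named in that sentence.

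**A reader might infer that the pooled interval will be too narrow, because one child can supply both doses.** The documents do not say that repeat values will be treated as independent. Section 9.4.1 plans a population PK model, and the SAP supplied covers only Part 2 and refers to a main SAP that was not available. What stands is that independence is a best case.

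**A reader might infer that the Group 3 dose was chosen on 8 observations.** Section 8.5 is prospective, extra infants were allowed, and the documents do not report how many observations were obtained.

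**The options to add infants or pool age groups could ease the shortfall.** They could, but no precision figure is attached to them.

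**Conclusion.** The precision statement is wrong as written for Group 3. At the plan's own CV, 8 independent observations give 63-159% instead of 71-141%, and a 36% probability (39% against 141%) instead of 80%. This rests on log-normality, independent observations and the t-interval method recovered from the printed figure. If one child supplies both doses and the two values are positively correlated, the true precision is worse.

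The statement for 12 observations is not at fault. Its gap against a literal 140% (77%) is marginal, and the printed 141% already shows it.

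Severity is minor. Part 1 is complete, dose selection in Section 3.7 rests on exposure compared with adults and on exposure-response, and nothing here questions a dose.

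**What to change.** In Sections 9.4.1 and 9.7:

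- State that 80% probability and 71-141% apply to 12 independent observations at CV 49.6%.
- Add a Group 3 sentence: about 8 observations give 63-159%, with a 36% probability of lying within 60-140% at CV 49.6%, assuming independent observations, which is a best case if one child supplies both doses.

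The cost is one clarified and one added sentence in each of two sections. No patients, data or analyses are added. The only downside is a less favourable stated precision for Group 3.

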#### 4 **Population**

The study population consists of pediatric HF patients 1 month to < 18 years, inpatient or outpatient, with systemic left ventricle systolic dysfunction (LVEF ≤45% or a fractional shortening  $\leq 22.5\%$ ). For inclusion criteria details regarding LVEF and fractional shortening, refer to Section 4.1. The study will enroll at least 18 patients in Part 1 and 360 patients in Part 2 (Efficacy) at centers worldwide. With an expected screen failure rate of 35% for both Part 1 (PK/PD) and Part 2 (Efficacy), it is estimated that approximately 46 patients will have to be screened for Part 1 and 554 patients will have to be screened for Part 2.

For Part 1, at least 18 subjects will be divided across three groups based on age: **Group 1**: 6 to < 18 years (6 observations for the LCZ696 0.8 mg/kg dose and 6 observations for the LCZ696 3.1 mg/kg dose); Group 2: 1 to < 6 years (6 observations for the LCZ696 0.8 mg/kg dose and 6 observations for the LCZ696 3.1 mg/kg dose); **Group 3**: 1 month to < 1 year (approximately 4 observations for LCZ696 -0.4 mg/kg dose and approximately 4 observations for the LCZ696 1.6 mg/kg dose). Eligible patients will participate in the LCZ696 0.8 mg/kg and 3.1 mg/kg doses in Groups 1 and 2 and in the LCZ696 0.4 mg/kg and 1.6 mg/kg doses in Group 3. Patients who do not participate in the LCZ696 3.1 mg/kg (Group 1 or 2) or 1.6 mg/kg (Group 3) dose will be replaced. To ensure that patients are enrolled in both high and low end of the 6 to < 18 years of age group, approximately 50% patients will be enrolled who are 6 to 11 years of age in Group 1.

For Part 2, patients will be stratified by age (Age Groups 1, 2 and 3) and NYHA/Ross class group (Class I/II, Class III/IV) at randomization to ensure a balanced distribution of treatment allocation within each age group. Patients who discontinue from Part 2 will not be replaced.

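### The Part 1 precision claim for Groups 1 and 2 treats 12 observations as independent, but the plan takes them as two doses from each of at least 6 children, so the stated 80% does not hold for the planned minimum

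*Protocol*

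**What the plan says.** - **Precision claim.** Section 9.7, Part 1: "Therefore, 49.6% of CV% was assumed for sample size estimations". The size is then given in observations, not patients: "A sample size of 12 observations (except Group 3 where", the Group 3 figure being about 8. The protocol says that this size "is expected to have 80% probability that the 95% CI of the point estimate for the geometric mean estimates". The target limits follow, for two named parameters: "of clearance and volume of distribution will be between 60% and 140% range". The printed 95% CI that results is 71-141%, and section 9.4.1 repeats the claim.
- **Source of the observations.** Section 3.1 plans at least 6 patients in each of Groups 1 and 2, with 6 observations at 0.8 mg/kg and then 6 at 3.1 mg/kg. For Group 1: "The patients who receive the LCZ696 single dose of 0.8 mg/kg treatment will also have an option to subsequently receive the LCZ696 3.1 mg/kg dose"; Group 2 has the same option. Another patient is recruited only when one does not qualify for, or declines, the higher dose. Section 4 makes two doses per child the expected course: "Eligible patients will participate in the LCZ696 0.8 mg/kg and 3.1 mg/kg doses in Groups 1 and 2".
- **Pooling.** Section 3.5: "For the estimation of precision for pharmacokinetic parameters, data obtained from both dose levels will be pooled". Section 9.6: "dose-normalized PK parameters from both dose cohorts will be combined". Section 9.6 also allows two age groups to be pooled if no age effect on PK is seen.
- **Not stated.** No within-patient correlation is given, and nothing says how a CI for the pooled geometric mean allows for two values from one child.

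**The concern.** Two clearance or volume values from the same child share that child's own level, so they carry less information about the group mean than values from two children. A calculation with 12 independent values and 11 degrees of freedom describes a study of 12 children. The planned minimum is six, with 5 degrees of freedom between children.

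Sections 9.4.1 and 9.7 contain the only precision statement behind the Part 1 PK estimates, which support the Part 2 dose for each age group. If it describes a different design, a reader is told that paediatric exposure is pinned down more closely than the plan can deliver. This point concerns Groups 1 and 2; the smaller Group 3 is a separate matter.

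**Working it through.** **Inputs.** CV 49.6%, 12 observations, 80% probability, limits 60-140% and the 71-141% interval (section 9.7); CVs of 39.4% for clearance and 37.1% for LBQ657 exposure (sections 9.4.1 and 9.7); at least 6 children with two doses each (sections 3.1 and 4). The within-child correlation ρ is an assumption, shown from 0.3 to 0.9.

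**1. Reproduce the printed figure.**
- Log-scale SD: σ = √ln(1 + 0.496²) = 0.469.
- For n independent values the log half-width is t(0.975, n−1)·s/√n, where (n−1)s²/σ² is χ² on n−1 df.
- For n = 12: t = 2.201 and the 80th percentile of χ² on 11 df is 14.63. The half-width reached with 80% probability is 2.201 × 0.469 × √(14.63/11)/√12 = 0.344, so the limits are 70.9-141.0%. This matches the printed 71-141%.
- P(upper limit ≤ 141%) = Pr{χ²₁₁ ≤ 11 × [0.3436 × 3.464/(2.201 × 0.469)]²} = Pr{χ²₁₁ ≤ 14.6} = 0.80.
- At a strict 140% the same formula gives 0.77. The upper limit is the binding one: an interval reaching 140% reaches only 71% on the low side.

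**2. Six children measured twice.** The log mean of a child's two values has SD σₚ = σ√((1+ρ)/2). With k = 6 children, df = 5 and t = 2.571:

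P = Pr{χ²₅ ≤ 5 × [ln(1.40)·√6/(2.571·σₚ)]²}

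Worked at ρ = 0.5: σₚ = 0.469 × √0.75 = 0.406. The bracket is 0.3365 × 2.449/(2.571 × 0.406) = 0.789, so 5 × 0.789² = 3.12 and Pr{χ²₅ ≤ 3.12} = 0.32. The 80%-assurance half-width is 2.571 × 0.406 × √(7.289/5)/√6 = 0.515, giving 60-167%.

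| ρ | P, CV 49.6% | P, CV 39.4% | P, CV 37.1% | 80%-assurance limits, CV 49.6% |
|---|---|---|---|---|
| 0.3 | 39% | 64% | 71% | 62-161% |
| 0.5 | 32% | 55% | 62% | 60-167% |
| 0.7 | 26% | 48% | 55% | 58-173% |
| 0.9 | 22% | 41% | 48% | 56-178% |

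All probabilities use the 140% limit. At CV 49.6%, using 141% instead gives 41%, 34%, 28% and 23%. At ρ = 0 the same patient-level analysis gives 54%.

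**3. More children, CV 49.6%.**
- Nine children, three of them measured twice: the effective number is 6/(1+ρ) + 6, with 8 df. The probability is 62% (ρ 0.3) down to 51% (ρ 0.9) at the 141% limit.
- Twelve different children: 80% at 141%, as in step 1.
- Groups 1 and 2 pooled, 12 children measured twice: the step 2 formula with k = 12 and 11 df gives 97%, 93%, 88% and 81% at ρ = 0.3, 0.5, 0.7 and 0.9 (140% limit).

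**4. If a CI treated six pairs as 12 independent values.** The true variance of the mean is σ²(1+ρ)/12, while the expected sample variance is σ²(1−ρ/11). Simulation (200,000 draws) gives coverage of a nominal 95% interval of 91.5%, 89%, 86% and 82% at ρ = 0.3, 0.5, 0.7 and 0.9. A patient-level interval would be wider by about (2.571/2.201) × √((1+ρ)/(1−ρ/11)), which is 1.46 times at ρ = 0.5 and 1.68 times at ρ = 0.9.

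**The case against.** - **Six is the minimum, not the forecast.** Section 3.1 says at least 6. The higher dose needs a minimum prior ACEI/ARB dose that the lower dose does not, so some replacement is foreseeable. Section 4 expects 46 children screened with 35% failing, and 46 × 0.65 ≈ 30 against a minimum of 18, which may budget for replacements. This stands, so the six-child figures must be labelled as the planned minimum. It does not restore the claim: nine children still fall short at CV 49.6%, and nothing in the plan requires 12 per group.
- **49.6% is the largest of the three CVs.** True, and at 37.1% with ρ = 0.3 six children reach 71%. But 49.6% is the value that the plan itself uses for the printed result.
- **The correlation is assumed.** True; the range has to be shown with the figures. Even ρ = 0 gives 54% for six children, because only 5 df remain.
- **Pooling Groups 1 and 2 would rescue it.** It would, but section 9.6 makes this conditional on no age effect, and it would no longer be age-specific precision.
- **The pooled CI may be handled properly.** A reader might infer that the plan's own 95% CI is too narrow. The documents do not support that: sections 3.5 and 9.6 say the values are combined but not how a CI is formed. The protocol summary describes descriptive summaries by age group and dose, where each child contributes one value per dose. Sections 6.6.2 and 9.4.1 also plan population PK modelling, and a model with a patient effect would avoid the fault. The SAP supplied is a regional supplement on Part 2 that refers to a main SAP not available here. The under-coverage in step 4 is therefore conditional.
- **No decision rule uses 60-140%.** Correct. Section 3.7 sets the Part 2 dose from exposure relative to adults and from neprilysin exposure-response. Section 8.5 adds safety review and a joint decision by the sponsor and the DMC, and Group 2 has further sparse PK sampling in Part 2. A reader might infer that the Part 2 doses rest on a faulty calculation; the documents do not support that.

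**Conclusion.** The point holds for the stated precision. The 80% and 71-141% in sections 9.4.1 and 9.7 are the result for 12 independent children, and the plan's minimum of six children measured twice does not have that property. For six children and ρ of 0.3-0.9, the probability of staying within 60-140% is about 39-22% at CV 49.6%, 64-41% at 39.4% and 71-48% at 37.1%. These figures rest on an assumed correlation, on exactly six children and on patient-level analysis, so a flat statement that the probability falls to 20-40% would go too far. At CV 49.6% the printed 80% requires 12 different children per group, or the conditional pooling of Groups 1 and 2.

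Whether any reported CI is too narrow cannot be judged from these documents. The amendment rationales record Part 1 as complete in all age groups, so what remains open is the written justification and how the CIs are computed and reported. The Part 2 primary analysis is not touched.

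**What to change.** - **Sections 9.4.1 and 9.7:** for Groups 1 and 2, replace the 80% / 71-141% claim with precision stated by number of children. For six children at CV 49.6%, give 80%-assurance limits of about 60-167% at an assumed correlation of 0.5, ranging from 62-161% (0.3) to 56-178% (0.9), and show the gain from replacement children.
- **Sections 3.5 and 9.6:** state that any CI for the pooled dose-normalised geometric mean uses patient-level means, or a mixed model on the log scale with a random patient effect.

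The cost is wording and one model term. The stated precision becomes less favourable, and CIs will be wider than ones that ignore the pairing. No patients, samples, doses or clinical rules change.
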